# 4.11.6 Vital Signs

Vital sign parameters will be presented for each treatment group based on SS.

Blood pressure and pulse rate will be assessed at the study site, as outlined in the SoA (Appendix A: Schedule of Activities), prior to blood collection for laboratory tests with the patient resting in a supine position using a completely automated device. Manual techniques will be used only if an automated device is not available.

Blood pressure and pulse measurements should be preceded by at least 5 minutes of rest for the patient in a quiet setting without distractions (e.g., television, cell phones) and will consist of 1 pulse and 3 BP measurements (3 consecutive BP readings will be recorded at intervals of at least 1 minute). The average of the 3 BP readings will be recorded on the eCRF.

Notable changes from pre-dose at each post-dose time point for vital sign parameters will be identified. The predefined criteria for notable changes in vital signs values are displayed in Table 7

Table 5 PCS vital signs predefined criteria

Vital sign	Level	Observed value	Notable change from baseline
Systolic BP (mmHg)	High	≥ 140	Increase of $\geq 20$
	Low	< 90	Decrease of $\geq 20$
Diastolic BP (mmHg)	High	≥ 90	Increase of $\geq 10$
	Low	< 60	Decrease of $\geq 10$
Pulse Rate (bpm)	High Low	≥ 100 < 50	Increase of $\geq 20$ Decrease of $\geq 20$

BP = Blood pressure.

The following summaries will be presented:

- A summary of the observed values and change from baseline in each vital sign parameter by treatment group and time point.
- A summary of key participant information for participants reporting notable changes outside predefined criteria in each vital sign parameter
- A summary of the number and percentage of participants experiencing notable changes from baseline outside predefined criteria, by vital sign parameter and treatment group.

By-participant listings of vital signs results, and findings will be provided.

# 4.11.7 Physical Examinations

A by-participant listing of physical examinations will be provided including date of examination and confirmation of assessment performed (Yes/No).

# 4.11.8 Safety Unblinded Data Review Committee

A Safety Unblinded Data Review Committee will be set up for this study for ongoing safety monitoring. In addition to general safety/tolerability, the committee will focus on potential risks related to hyperkalaemia, hypotension and deteriorating renal function.

### 4.12 Other Analyses

#### 4.12.1 Pharmacokinetics

Summary statistics for the PK concentrations will include number of observations, number of observations below the lower limit of quantification (LLOQ), geometric mean, GeoCV, arithmetic mean, arithmetic standard deviation, median, minimum, and maximum. Any concentrations that are not reportable or where no sample is available will be excluded from the summary tables. Three observations > LLOQ are required as a minimum for plasma concentrations at a specific time point to be summarised. Two observations > LLOQ are presented as minimum and maximum with the other summary statistics as not calculated. For PK concentration summaries, at a time point where less than or equal to 50% of the values are below LLOQ, values will be set to the LLOQ/2, and all descriptive statistics will be calculated.

Plasma concentrations of AZD9977 and dapagliflozin will be listed and summarised by treatment groups and visit, based on the PK Analysis Set. Plasma concentrations of AZD9977 and dapagliflozin will be measured throughout the study as described in Appendix A: Schedule of Activities.

The pre-dose plasma concentrations of AZD9977 and dapagliflozin will be summarised, separately, by descriptive statistics for each visit and each sample point for AZD9977-treated participants by treatment. To illustrate pre-dose plasma concentrations, a graph with boxplots will be generated, drawn against visit number (i.e. three boxplots corresponding to each of the visit with pre-dose PK collection; only pre-dose concentrations for Visit 7). One plot will be generated per each treatment group and analyte (two analytes: AZD9977 and dapagliflozin).

Separate summary statistics will be provided for each sampling time in the PK post-dose subgroup (Visit 7). Samples are to be taken 1 ( $\pm 0.25$ ), 2 ( $\pm 0.25$ ), 4 ( $\pm 0.5$ ), and 6 ( $\pm 1$ ) hours post-dose. Graphically, geometric-mean curves will be plotted against nominal time (±geometric standard deviation); two plots will be prepared per each analyte (AZD9977 and dapagliflozin): one on a linear scale and one on a semi-logarithmic scale. Pre-dose PK sample collected at Visit 7 will also be included in the summary statistics and when generating the

A by-participant listing of drug concentration data of AZD9977 and Dapagliflozin will be provided for all randomised participants. Individual concentrations below the LLOQ will be reported as non-quantifiable (NQ) in the listings with the LLOQ defined. Individual plasma concentrations that are Not Reportable (NR) will be reported as NR and those that are missing will be reported as NS (No Sample) in the listings.

TP-GDO-WW-016-08 CONFIDENTIAL Effective Date: 26 Nov 19 Related to: SOP-GDO-WW-019

Page 36 of 50

#### 4.12.2 Pharmacodynamics

The following summaries will be provided for the pharmacodynamic and biomarker variables by treatment group based on the PD set:

- Observed absolute values and change from baseline in plasma/serum uric acid, BUN, FPG, haematocrit, renin, ACTH, cortisol and copeptin levels by treatment group and time point.
- Observed absolute values and change from baseline in blood MCV, MCHC, RBC distribution width, erythrocyte count by treatment group and time point.
- Observed absolute values and change from baseline in urine Na+, K+, uric acid, urea, osmolality, glucose, creatinine, and cortisol levels by treatment group and time point.
- Observed absolute values and change from baseline in blood and urine biomarkers by treatment group and time point
- A by-participant listing of pharmacodynamic variables will be provided for all the randomised participants.

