Procedure	Pre- scre enin g	Screeni ng	Start Run-in	Pre- rando- misation	Baseline/ Rando misation			Treatm	ient Pe	riod		EOT/ET a	Safety Follow-u p	Notes	Details in CSP Section or Appendix
Visit ^b	Opti onal	1a	1b	2	3	4	5	6	7	8	9	10	11		-
Week	c	(-8 to -7)* -6 to -5	(-7 to -6)* -5 to -4	-1	1	1	2	3	4	7	10	13	17	* Applies to SGLT2i naïve	For details on run-in period see
Day	c	(-56 to -49)* -42 to -35	(-49 to -42)* -35 to -28	-10 to -3	1	3 ± 1	8 ±2	15 ±3	22 ±3	43 ±3	64 ±3	85 ±3	113 ±4	patients	Section 4.1
Central laboratory serum sample for creatinine for eGFR calculation				X °											Section 8.2.4
Central laboratory serum sample for cystatin C for eGFR calculation				X °	X (pre- dose)	х	х	X	Х	X	Х	х	Х		Section 8.2.4
Central laboratory blood samples for HbA1c, cholesterol, and lipids					X (pre- dose)							X	х	After at least 8-hour fasting for lipids.	Section 8.2.4
Central laboratory urinalysis					X (pre- dose)					Х		Х	х		Section 8.2.4

Procedure	Pre- scre enin g	Screeni ng	Start Run-in	Pre- rando- misation	Baseline/ Rando misation			Treatm	ient Pe	riod		EOT/ET a	Safety Follow-u p	Notes	Details in CSP Section or Appendix
Visit ^b	Opti onal	1a	1b	2	3	4	5	6	7	8	9	10	11		
Week	c	(-8 to -7)* -6 to -5	(-7 to -6)* -5 to -4	-1	1	1	2	3	4	7	10	13	17	* Applies to SGLT2i naïve	For details on run-in period see
Day	c	(-56 to -49)* -42 to -35	(-49 to -42)* -35 to -28	-10 to -3	1	3 ± 1	8 ±2	15 ±3	22 ±3	43 ±3	64 ±3	85 ±3	113 ±4	patients	Section 4.1
Central laboratory urine samples for albumin, creatinine (for UACR calculation), Na ⁺ , K ⁺ , uric acid, urea, osmolality, glucose, and cortisol ^f				X e, f			x		X	X	х	x	X	First morning void urine sample collected at home in provided vials over 3 consecutive days until the visit day.	Sections 8.1.1, 8.5.2, 8.6.1
Pharmaco- kinetics															
Predose sample for AZD9977 and dapagliflozin plasma concentrations							X		x			X		Collected before dose intake at site, or 1 day after last dose for the EOT/ET visit.	Section 8.5.1

Procedure	Pre- scre enin g	Screeni ng	Start Run-in	Pre- rando- misation	Baseline/ Rando misation			Treatn	ient Pe	riod		EOT/ET a	Safety Follow-u p	Notes	Details in CSP Section or Appendix
Visit ^b	Opti onal	1a	1b	2	3	4	5	6	7	8	9	10	11		
Week	c	(-8 to -7)* -6 to -5	(-7 to -6)* -5 to -4	-1	1	1	2	3	4	7	10	13	17	* Applies to SGLT2i naïve	For details on run-in
Day	c	(-56 to -49)* -42 to -35	(-49 to -42)* -35 to -28	-10 to -3	1	3 ± 1	8 ±2	15 ±3	22 ±3	43 ±3	64 ±3	85 ±3	113 ±4	patients	period see Section 4.1

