4.2 Scientific Rationale for Study Design

The study is designed to evaluate the effect of AZD9977 in combination with dapagliflozin compared with dapagliflozin alone on UACR. The secondary objective is to assess the dose-response relationship of dapagliflozin (10 mg) alone and 3 doses of AZD9977 (15, 50, or 150 mg) combined with dapagliflozin (10 mg) on UACR.

The primary endpoint (percent change from baseline in UACR at 12 weeks) is an established key surrogate marker of the MRA mechanism of action. This marker has also shown to be predictive for adverse cardiovascular outcomes in patients with HF (Selvaraj et al 2018). Reported studies have shown a clear dose-response with UACR for MRAs (eg, finerenone), unlike other biomarkers relevant for HF such as the cardiac biomarker NT-proBNP. Clear effects on UACR have also been established for dapagliflozin (Pollock et al 2019), while dapagliflozin did not significantly reduce NT-proBNP over 12 weeks compared with placebo (Nassif et al 2019).

The study will evaluate general safety and tolerability with special focus on serum/plasma K⁺, eGFR, and hypotension of treatment with AZD9977 and dapagliflozin in combination and alone. Exploratory objectives include PK, NT-proBNP, biomarkers reflecting cardiac fibrosis, endothelial function, and other aspects of cardiovascular function as well as markers of the potential mechanisms of action of SGLT2 inhibitors and AZD9977.

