8.1 Efficacy Assessments

8.1.1 Primary/Secondary Variable: Urinary Albumin to Creatinine Ratio (UACR)

The UACR is calculated as follows:

• UACR (mg/mmol) = $10 \times$ urine albumin (mg/dL) / urine creatinine (mmol/L)

Urine samples for the determination of albumin and creatinine and calculation of UACR will be collected at the timepoints described in the SoA:

- After consent at screening (Visit 1a), a container to collect the spot urine sample will be dispensed to the participants. The spot urine sample will be collected at this visit.
- Collection of triplicate urine sampling will start at Visit 2. At Visit 1b and at subsequent visits, containers to collect the urine samples will be dispensed to the participants prior to the visits described in the SoA. Investigators will perform a phone call prior to the visit to remind the participants to collect the first morning void samples. Participants will collect first morning void urine samples at home on 3 consecutive days (ideally day of visit and

preceding 2 days [refrigerated overnight] which will be returned on the day of visit). Samples will be analysed centrally. At each visit, the geometric mean of the triplicate measurements will be computed centrally and used for all analyses of UACR.

Note: The samples collected on visit days will also be used for the determination of exploratory urinary parameters (see Section 8.5.2.1 and 8.6.2).

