8.5.2.1 Collection of Samples

Urine Samples

Urine samples will be collected and analysed at a central laboratory for the determination of the exploratory urinary parameters at the timepoints specified in the SoA.

The urine samples collected on visit days for the analysis of UACR (see Section 8.1.1) will be split, so that it can also be used for the determination of Na^+ , K^+ , uric acid, urea, osmolality, glucose and cortisol levels.

Blood Samples

Blood samples will be collected at the timepoints specified in the SoA and analysed at a central laboratory for the determination of the following parameters:

- NT-proBNP, aldosterone, active renin, ACTH, cortisol, and copeptin
- FPG (for fasting conditions, see Section 5.3.1)

In addition, blood samples will be collected at screening and analysed locally for the determination of NT-proBNP to confirm eligibility criteria.

Samples will be collected, labelled stored and shipped as detailed in the Laboratory Manual.

For storage, re-use and destruction of pharmacodynamic samples see Section 8.5 and Appendix C.

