9.4.4 Pharmacodynamics and Biomarkers

The following exploratory pharmacodynamic and biomarker endpoints will be summarised by treatment group based on the FAS:

- Change from baseline in serum NT-proBNP over time
- Change from baseline in blood uric acid, BUN, FPG, haematocrit, renin, ACTH, cortisol and copeptin levels over time
- Change from baseline in blood MCV, MCHC, RBC distribution width, erythrocyte count over time
- Change from baseline in urine Na⁺, K⁺, uric acid, urea, osmolality, glucose, creatinine, and cortisol levels over time
- Change from baseline in blood and urine biomarkers over time

The following analyses will not be part of the CSR:

- Dose/exposure of AZD9977 and dapagliflozin relative to safety and pharmacodynamic variables (eg, serum/plasma K⁺, eGFR, aldosterone)
- Exploratory research into genes/genetic variation that may influence response to treatment

Analysis for these exploratory objectives will be described in a separate analysis plan and results will be presented separately from the main CSR.

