# 3.2.3 Exploratory Endpoints

- Percentage change from baseline in serum NT-proBNP over time
- Plasma concentrations of AZD9977 and dapagliflozin
- Dose/exposure of AZD9977 and dapagliflozin relative to safety and pharmacodynamic variables (e.g., serum/plasma K+, eGFR, aldosterone)
- Change and percentage change from baseline in blood uric acid, BUN, fasting plasma glucose (FPG), haematocrit, renin, ACTH, cortisol and copeptin levels over time
- Change and percentage change from baseline in blood MCV, MCHC, RBC distribution width, erythrocyte count over time
- Change and percentage change from baseline in urine Na+, K+, uric acid, urea, osmolality, glucose, creatinine, and cortisol levels over time

TP-GDO-WW-016-08 CONFIDENTIAL Project Document Version No. 3.0 Effective Date: 26 Nov 19 Project Document Effective Date: Date of last signature Related to: SOP-GDO-WW-019 Page 13 of 50

- Evaluation of changes in blood biomarkers (including but not limited to hsTnT, PIIIP3, GDF-15, ST2, ADMA, SDMA, L-Arg, ICAM, NGAL) over time
- Biomarker assessment in serum, plasma, and urine samples
- Evaluation of changes in blood biomarkers (including but not limited to hsTnT, PIIIP3, GDF-15, ST2, ADMA, SDMA, L-Arg, ICAM, NGAL) over time

Exploratory research into genes/genetic variation that may influence response to treatment

# 3.2.4 Analysis of Cohort 1

The following summaries will be reported separately for Cohort 1:

- Demographics characteristics
- Baseline characteristics
- Disease characteristics
- Vital signs
- Prior and concomitant medications
- Adverse Events

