# 4.10.1 Primary/Secondary Endpoint

The primary efficacy endpoint for this study is the percent change from baseline in UACR at the end of 12 weeks of study treatment (Visit 10).

Central laboratory urine samples for the determination of albumin and creatinine and calculation of UACR will be collected at the timepoints described in the SoA (Appendix A: Schedule of Activities).

Participants will collect 1st morning void urine samples at home on 3 consecutive days (ideally day of visit and preceding 2 days [refrigerated overnight] which will be returned on the day of visit).

The UACR from each urine sample will be calculated as follows:

$$UACR (mg/mmol) = 10 \times \frac{Urine \ Albumin (mg/dL)}{Urine \ Creatinine (mmol/L)}$$

At each visit, the geometric mean of the triplicate UACR values will be computed and used for the analysis of UACR. In case of missing values for UACR the geometric mean will be calculated considering the number of the available measurements. Baseline for UACR will be defined as the geometric mean of 3 consecutive days prior to the first dose of study treatment (ideally day of visit and preceding 2 days). Only samples collected prior to the first dose of study medication will be used.

As UACR is assumed to follow a log-normal distribution, it will be log transformed for statistical analysis purposes obtaining the ratio of geometric means.

Percent change from baseline in UACR at  $Visit_k$ , k in  $\{7, 8, 9, 10\}$  will be calculated as:

$$100 \times \left(\frac{GeoMean(UACR_{Visit_k})}{GeoMean(UACR_{Baseline})} - 1\right)$$

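### The exploratory urine solute summaries use unnormalised levels from one untimed void, so they cannot separate a change in excretion from a change in urine dilution

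*SAP*

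**What the plan says.** **Planned output.** SAP 4.12.2 tabulates the recorded value and its difference from baseline for sodium, potassium and the remaining urine analytes: "uric acid, urea, osmolality, glucose, creatinine, and cortisol levels by treatment group and time point". SAP 3.2.3 words the endpoint as "Change and percentage change from baseline in urine Na" and the other analytes, which adds a percentage change that 4.12.2 does not carry through. Protocol Table 3 and Section 9.4.4 also refer to change in "uric acid, urea, osmolality, glucose, creatinine, and cortisol levels over time".

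**Specimen.** The Schedule of Activities (Protocol 1.3) specifies: "First morning void urine sample collected at home in provided vials over 3 consecutive days until the visit day". Neither document describes a void volume, a collection interval or a timed collection.

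**Which void is used.** UACR takes the geometric mean of three voids. For the other analytes, Protocol 8.1.1 states: "The samples collected on visit days will also be used for the determination of exploratory urinary parameters". Protocol 8.5.2.1 adds: "The urine samples collected on visit days for the analysis of UACR (see Section 8.1.1) will be split". Each analyte therefore rests on one void per visit, and urine creatinine is available from that same void.

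**Existing correction.** SAP 4.10.1 divides albumin by creatinine sample by sample ("The UACR from each urine sample will be calculated as follows"). No other urine variable in either document is divided by creatinine, adjusted for osmolality, or expressed as a Na+/K+ ratio or fractional excretion.

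**The concern.** A solute concentration in an untimed void depends on how much solute was excreted and how much water went with it. If volume changes, every concentration moves in the same direction although no solute is being handled differently. If solute and water rise together, concentration does not move at all.

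These analytes are measured for a mechanistic reason. Protocol 4.2 describes the exploratory markers as including "markers of the potential mechanisms of action of SGLT2 inhibitors and AZD9977", and Protocol 2.2.1.3 discusses whether the dose-response for urinary electrolyte excretion differs from that for organ protection. Excretion is the quantity of interest there, and concentration is an imperfect stand-in for it.

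What is at stake is the interpretability of one set of exploratory tables. The trial corrects for dilution in albumin and has the same denominator available for the other solutes, but does not plan to use it.

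**Working it through.** The plan states no figure on this point, so there is nothing to reproduce. The calculations below are illustrations, and every effect size and SD in them is an assumption. Only n = 119 evaluable participants per arm comes from the documents (Protocol 9.2).

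**1. What a concentration comparison estimates.** Let x be the relative between-arm difference in solute excretion and v the relative between-arm difference in urine volume.

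- Concentration difference = (1 + x)/(1 + v) - 1
- Solute/creatinine difference = x, if creatinine excretion is unchanged

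| True x | v = -10% | v = 0 | v = +10% | v = +20% | v = +30% |
|---|---|---|---|---|---|
| 0% | +11.1% | 0.0% | -9.1% | -16.7% | -23.1% |
| +20% | +33.3% | +20.0% | +9.1% | 0.0% | -7.7% |

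For example, 1.2/1.2 - 1 = 0% and 1/1.2 - 1 = -16.7%. The creatinine ratio gives 0% across the first row and +20% across the second. Concentration equals the excretion effect only when v = 0; otherwise the effect can be inflated, shrunk, cancelled, reversed or created.

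**2. What happens if dilution is purely random.** There is then no systematic difference in v and no bias, but the variance grows. Assume a log-scale SD of change of 0.4 without dilution, and an independent dilution log-SD of s at each of the two visits forming the change:

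- Total SD = sqrt(0.4² + 2s²)
- SE of the arm difference = total SD × sqrt(2/119)

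| s | Total SD | Power for a true 20% difference, two-sided 0.05 |
|---|---|---|
| 0 | 0.400 | 94% |
| 0.2 | 0.490 | 82% |
| 0.3 | 0.583 | 67% |
| 0.4 | 0.693 | 53% |
| 0.5 | 0.812 | 41% |

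At s = 0.3 the SE rises from 0.400 × 0.1296 = 0.052 to 0.583 × 0.1296 = 0.076. No test is planned for these analytes, so power serves here only as a measure of lost precision. The calculation assumes that all 119 participants per arm supply both samples.

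**3. What the planned creatinine table can show.** With x = v = +20% and creatinine excretion unchanged, mean Na+ concentration is flat while mean creatinine concentration falls by 16.7%. A careful reader could see this. The tables would still leave each patient's Na+ value uncorrected.

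**The case against.** A reader might infer that the tables cannot show any drug effect on urine electrolytes. The documents do not support that. Allocation is 1:1:1:1, every arm receives dapagliflozin 10 mg, and collection is identical across arms (Protocol 4.1, 8.1.1). Dilution unrelated to treatment is noise in the arm comparison. Bias needs AZD9977 itself to alter urine water output, and no section shows that it does.

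A reader might also blame the background loop diuretic or SGLT2 inhibitor. Dapagliflozin, however, is started or continued for 4 to 7 weeks before randomisation, so its effect is already present at the Visit 2 urine baseline. Background heart failure treatment is meant to be stable (Protocol 6.5.2), and randomisation balances both in expectation.

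Nor is the stated objective left unanswered. It concerns the effect on urine analytes, with change in levels as the endpoint; excretion rate is not named. The hyperkalaemia question has its own serum K+ analyses.

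Urine creatinine and osmolality are tabulated by arm and visit, so a mean shift in dilution would show. SAP 4.2 also plans geometric means for log-normal variables. On identical samples, the quotient of two geometric means is the geometric mean of the ratio. The SAP does not say which urine analytes are treated as log-normal, however, and the quotient gives no spread for the ratio.

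Finally, the table shells and the separate dose/exposure-response plan are not in the text reviewed, and no units are given for the levels.

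All of this limits the concern. It does not remove the narrow point: the written plan contains no per-patient correction for dilution.

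**Conclusion.** The concern holds in a limited form: as written, the summaries cannot separate a change in solute excretion from a change in urine dilution. If dilution is random, the cost is precision; in the illustration, power falls from 94% to 67% at a per-visit dilution log-SD of 0.3. If AZD9977 changes urine volume, the comparison is biased as an estimate of excretion; a 20% volume difference would cancel a true 20% rise or produce a false 16.7% fall. The documents neither establish nor exclude such a change in volume, and the sizes used are assumptions.

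The conclusion rests on reading levels as concentrations, which is the natural reading. It applies to Na+, K+, uric acid, urea, glucose and cortisol. Osmolality and creatinine are themselves markers of dilution. These are exploratory, descriptive endpoints, so this is a cheap improvement and not a threat to the trial's conclusions.

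**What to change.** In SAP 3.2.3 and 4.12.2:

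- Keep the summaries of levels. Protocol 9.4.4 specifies them by treatment group, so moving them to listings would drop a protocol-specified output.
- Add the ratio to urine creatinine, from the same visit-day void, for Na+, K+, uric acid, urea, glucose and cortisol. Summarise it on the log scale as geometric mean ratio to baseline, by arm and visit.
- Add the urine Na+/K+ ratio, in which dilution cancels without any assumption about creatinine.
- Record the ratios in SAP 4.14 as added exploratory summaries. Settling them before unblinding avoids choosing a normalisation after seeing results.

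The cost is a few derived variables and table shells, with no new samples or assays. The creatinine ratios assume that creatinine excretion is stable within a patient. Sodium and potassium intake is not controlled (Protocol 5.3.1), so the ratios will still vary with diet. Fractional excretion is possible, but the urine baseline is Visit 2 and the baseline central serum chemistry is Visit 3, so the pairing would have to be defined first.
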